7.6. PRIOR AND CONCOMITANT MEDICATIONS

A summary of medications taken during the course of the study will be presented in tabular form using Anatomical Therapeutic Chemical (ATC) classification level 2 and PT via the World Health Organization Drug Classification Dictionary (WHO-DD) version March 2012 or later. All medications will be summarized using the full analysis set by treatment group and sorted alphabetically by ATC level 2 class and PT.

Prior medications are those medications taken before the start of treatment in the single-blind run-in phase, not including medications ongoing at the start of the run-in. A medication is considered concomitant in the single-blind run-in phase if ongoing at or taken on or after the start date of treatment in the run-in. A medication is considered concomitant in the double-blind treatment phase if ongoing at or taken on or after the start date of study treatment. A medication can be concomitant in both the single-blind run-in and double-blind treatment phases. Concomitant medications will be summarized by the number and percentage of patients taking a particular medication using the coding described above by phase. If a patient has taken a medication more than once, the patient will be counted only once in the total. Prior medications will be listed only.

See Section 12.9 of the protocol for more details on the time frame allowed for medications.

All prior and concomitant medications will be listed on the safety analysis set by treatment group.

Medications with incomplete end dates will be considered concomitant, unless an incomplete date (e.g. month and year) clearly indicates that the medication started and stopped prior to the start of treatment:

- Day and month are missing and the year is equal to or after the year of the start of treatment in the run-in;

- Day is missing and the year is after the year of the start of treatment in the run-in;
- Day is missing and the year is equal to the year of the start of treatment in the run-in and the month is equal to or after the month of the start of the run-in;
- Year is missing; or
- Complete date is missing.

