3.4. BRIEF DESCRIPTION

This is a Phase 2, double-blind, parallel group, placebo-controlled, dose ranging safety and efficacy study of piromelatine in patients with mild dementia due to Alzheimer's disease (AD).

During the double-blind period, patients will be enrolled in a 1.2:1:1:1 randomization ratio to the 4 trial arms (placebo [1.2], and the equal piromelatine treatment arms 5,

20, and 50 mg [1:1:1]). Intermediate visits will be carried out at 4 weeks (Visit 3) and 13 weeks (Visit 4) after randomization.

Figure 1: Overall Study Design

Period	Screening	Single-blind Run-in		Double-blind Treatment			Follow-up Phone call
		Run-in	Randomization				
Week		-2	0	4	13	26	28
Visit	1		2	3	4	5	
Treatment		Placebo		Piromelatine 5, 20, or 50 mg or Placebo			N/A

Each patient will undergo a 2-week, single blind run-in period and a 26-week, randomized, double-blind treatment period, for a total of 28 weeks. Two weeks after last dosing of study medication, the patient will receive a follow-up phone call. The duration of the study is expected to be approximately 40 months from first patient screened to final patient completing the randomized treatment.

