4.4. SAFETY ENDPOINTS

The following variables will be collected for assessment of safety:

- Adverse events (including Serious Adverse Events [SAEs]);
- Physical examination;
- Vital signs;
- Concomitant medications;
- Laboratory parameters (hematology, biochemistry [including sex hormones], and urinalysis);
- Electrocardiograms (ECG);
- Sheehan Suicidality Tracking Scale (Sheehan-STS).

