5.5. PROTOCOL DEVIATIONS AND VIOLATIONS

A protocol deviation is any change or alteration from the procedures stated in the study protocol, consent document, recruitment process, or study materials (e.g., questionnaires).

A major protocol violation is a deviation that has an impact on subject safety, may

substantially alter risks to subjects, may have an effect on the integrity of the study data, or may affect the subject's willingness to participate in the study. Major protocol violations include (but are not limited to): deviation from inclusion/exclusion criteria, withdrawal criteria met during the study but subject was not withdrawn, prohibited concomitant medications, substantial deviations from the dosing schedule.

A minor protocol violation is a deviation that does not impact subject safety, compromise the integrity of the study data, or affect the subject's willingness to participate in the study.

Protocol deviations will be documented during the study period using the IMPACT monitoring database and will be assigned into one of the following categories:

- Visit schedule;
- Concomitant medication;
- Dosing;
- Laboratory;
- Non-compliance;
- Visit/procedures requirements;
- Other.

This data will be exported from IMPACT and a listing will be generated with the date of occurrence, the category (as above), type of violation, and the reason for the deviation. The listing will be reviewed prior to database lock.

All protocol deviation/violation data will be listed and summarized on the safety analysis set.

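### SAP Section 7.6 gives each phase's concomitant-medication rule a start date and no end date, so the run-in summary takes in every double-blind medicine

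*SAP*

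**What the plan says.** Section 7.6 of the SAP sets the scope of the tabulation first: "A summary of medications taken during the course of the study will be presented in tabular form". It then defines two phases.

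- Run-in rule, in the SAP's words: "considered concomitant in the single-blind run-in phase if ongoing at or taken on or after the start date of treatment in the run-in".
- Double-blind: "A medication is considered concomitant in the double-blind treatment phase if ongoing at or taken on or after the start date of study treatment".

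The section adds that one medication may belong to both phases, and it fixes the presentation: "Concomitant medications will be summarized by the number and percentage of patients taking a particular medication using the coding described above by phase". The output is Table 14.1.4, on the full analysis set. No post-treatment category is defined. For timing the section points elsewhere: "See Section 12.9 of the protocol for more details on the time frame allowed for medications".

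Three other parts of the SAP bear on this. Section 3.4 places a contact after treatment: "Two weeks after last dosing of study medication, the patient will receive a follow-up phone call". Section 6.2 defines a last dose date, which Section 7.6 does not use. Section 9.3 closes the treatment-emergent adverse event (TEAE) window 14 days after the last dose, and it separates run-in events from later ones at the first double-blind dose.

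**The concern.** A summary split by phase needs intervals with two ends, and both rules in Section 7.6 have one. The run-in comes before randomization, so its part of the table should describe what patients were taking before they received double-blind treatment. As worded it also takes in medicines first used months later, and the split no longer separates what it is meant to separate. At the other end, a medicine begun after study drug was stopped would be shown under the double-blind phase. Section 4.4 lists "Concomitant medications" among the safety variables, so the table will be read by treatment arm.

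**Working it through.** There is no figure in the plan to reproduce. The check is to apply the two rules as written.

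**Inputs.** From Section 3.4: run-in starts at Week -2, first double-blind dose at Week 0, last dose at Week 26 for a completer, follow-up call at Week 28. From Section 7.6: the two start-date rules. From Section 9.3: the TEAE window, last dose plus 14 days, which for a completer is Week 26 + 2 weeks = Week 28.

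**Step 1, the logic.** Let R be the run-in start and D the first double-blind dose, with R earlier than D. A medicine is double-blind concomitant if any use falls at or after D. Any use at or after D is also at or after R. So every double-blind concomitant medicine is also run-in concomitant. The only medicines found in the run-in part alone are those stopped before D.

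**Step 2, illustrative cases for a completer.**

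| Medicine | Run-in as written | Double-blind as written | With both phases closed |
|---|---|---|---|
| Taken only at Week -1 | yes | no | run-in |
| Started before Week -2, still ongoing after Week 0 | yes | yes | both |
| First taken at Week 13 | yes | yes | double-blind |
| First taken at Week 27, if recorded | yes | yes | post-treatment (cut-off at last dose) or double-blind (cut-off at last dose plus 14 days) |

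The first two rows come out as intended. The third row is misplaced whatever is assumed about data collection. The fourth is misplaced in the run-in part, and its double-blind placement depends on the cut-off chosen.

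**Step 3, consequence for the table.** Patients are counted once per medication. For any preferred term, the run-in count in an arm therefore cannot be smaller than the double-blind count in that arm.

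**Step 4, search for a limit elsewhere.** The incomplete-date rules in Section 7.6 act only at the lower end: they exclude medicines clearly started and stopped before treatment. The last dose date in Section 6.2 is not brought in. The reference to protocol Section 12.9 is worded as concerning what is permitted and when, not how records are sorted for the table. Nothing in the SAP supplies an end date for either phase.

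**The case against.** The best defence is that the phases are bounded by the design. Section 3.4 describes a 2-week run-in and a 26-week double-blind period and shows the follow-up call as a separate period. Saying that a medicine may be concomitant in both phases presupposes distinct intervals, and a sensible programmer would probably close them. That softens the consequence but leaves the text as it is. The rule states its own test, a medicine first taken at Week 13 passes the run-in test, and overlap that was meant to be possible becomes automatic.

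It can also be said that the table promises only medicines taken during the study and does not claim they were taken together with study drug, so an inclusive double-blind rule fits. This has force for medicines begun after the last dose. That part also requires such medicines to be recorded. The SAP does not say what the follow-up call collects, and neither protocol Section 12.9 nor the table shells are at hand.

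Two stronger readings are tempting.

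- A reader might infer that the loose rule could remove patients from the per protocol set, since Section 5.5 names "prohibited concomitant medications, substantial deviations from the dosing schedule" among major violations. The SAP does not support this. Deviations are captured by the monitoring team and classified case by case at the blinded data review meeting (Sections 5.5 and 7.2), and nothing ties that review to the Section 7.6 definition.
- A reader might infer that an arm with more withdrawals will appear to have used more medication on treatment, and try to put a percentage on it. The SAP gives no rate of new medicines after stopping, no withdrawal rate by arm and no recording period. The table is on the full analysis set, which omits patients without a post-baseline primary assessment, so a percentage of all randomized patients would not describe it.

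**Conclusion.** The point holds as a drafting error of small consequence. The run-in overlap follows from the wording alone: as written, the run-in part of Table 14.1.4 contains the whole of the double-blind part. The post-treatment gap is real in the text but weaker. It matters only if medicines begun after the last dose are recorded, and the documents do not settle whether the phase should end at the last dose or 14 days later.

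The effect stops at a descriptive table of counts and percentages. No efficacy or safety test uses it, and no size in percent can be derived from the SAP.

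**What to change.** In Section 7.6:

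1. Require that a run-in concomitant medication was started before the first double-blind dose. Medicines still ongoing at that dose stay in both phases.
2. Close the double-blind phase at a stated date built on the last dose date in Section 6.2. Either the last dose itself or the last dose plus 14 days, to match the TEAE window in Section 9.3, would do, provided the SAP names one.
3. List medicines started after that date as post-treatment.

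The cost is one clause per phase and a date condition in the program. There is one small downside. If the cut-off is the last dose date, medicines used for adverse events in the following 14 days appear only in the listing, while the events themselves still count as treatment-emergent. The 14-day extension avoids that mismatch, at the price of counting some medicines begun after dosing ended.

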9.3. ADVERSE EVENTS

Adverse events will be collected throughout the study, from informed consent until the end of the treatment period.

Adverse events will be summarized by the SOC and PT based on the MedDRA dictionary version 17.1 or later.

Treatment emergent adverse events (TEAEs) are defined as any adverse events (AEs) that occur after the start of administration of the first dose of study drug and through

14 days after the last dose of study drug, or any event that is present at baseline and continues after the first dose of study drug but worsens in intensity.

See Section 14.1 of the protocol for definition of serious adverse events (SAEs).

Treatment emergent AEs will be characterized based on the onset date relative to each patient's participation in the study.

Adverse events with incomplete start dates will be considered a TEAE if:

- Day and month are missing and the year is equal to or after the year of the first dose date;
- Day is missing and the year is after the year of the first dose;
- Day is missing and the year is equal to the year of the first dose date and the month is equal to or after the month of the first dose date;
- Year is missing; or
- Complete date is missing.

If the relationship to study treatment is missing then related will be used for the summaries. Similarly, events with missing intensity or severity will be counted as severe (Grade 3).

The summary tables will include the number of subjects and the number of events. Percentages will be based on the number of subjects. For summaries by SOC and PT, a patient will be counted once at the SOC level and once at each PT within the SOC level. For summaries by SOC, PT, and maximum severity, a patient will be counted once at the highest severity level for which the event occurred at the SOC level and the highest severity level for each unique PT within that SOC level. Therefore, patients may only contribute once to each PT and once to each SOC level.

The summaries presenting frequency of AEs by SOC and PT will be ordered by overall descending frequency of SOC and then, within a SOC, by overall descending frequency of PT.

The following AE tables will be provided:

- An overall summary of the number and percentage of patients reporting AEs, TEAEs, treatment-related TEAEs, severe TEAEs, serious TEAEs, treatment-related serious TEAEs, and TEAEs leading to withdrawal of study medication;
- TEAEs, overall and by SOC and PT;

- Serious TEAEs, overall and by SOC and PT;

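### Section 7.6 attaches its list of conditions for a concomitant medication to the exception for prior medications, so the incomplete-end-date rule inverts if coded literally (low severity)

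*SAP*

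**What the plan says.** Section 7.6 of the SAP sets a default, that a medication with an incomplete end date is concomitant, and an exception: "unless an incomplete date (e.g. month and year) clearly indicates that the medication started and stopped prior to the start of treatment". The sentence ends in a colon and is followed by five bullets:

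1. "Day and month are missing and the year is equal to or after the year of the start of treatment in the run-in"
2. "Day is missing and the year is after the year of the start of treatment in the run-in"
3. day missing, same year as the run-in start, and "the month is equal to or after the month of the start of the run-in"
4. year missing
5. "Complete date is missing"

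The same section defines the classes. A prior medication was taken before run-in treatment began and was not ongoing at that point. A medication is concomitant in the run-in, or in the double-blind phase, if it was ongoing at the start of that phase or taken on or after it. Concomitant medications are summarized by phase, and prior medications are only listed.

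Section 9.3 has a list of the same five conditions for adverse event start dates, with first dose as the reference. Its lead-in is "Adverse events with incomplete start dates will be considered a TEAE if".

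Section 6.3 sends missing or partial medication dates to Section 7.6 and allows no other imputation.

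**The concern.** The colon makes the bullets read as the cases in which an incomplete end date shows that the drug stopped before treatment. None of them can show that. An end date in a later year shows the opposite, and a wholly missing date shows nothing. The conditions that make a medication concomitant have been placed under the clause that makes it prior.

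Because Section 6.3 points to this section and permits nothing else, Section 7.6 is the operative derivation rule. A programmer who codes it as punctuated would move records between classes in both directions. Prior medications are listed only, so a drug wrongly called prior leaves Table 14.1.4. Concomitant medication is one of the safety variables in Section 4.4.

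**Working it through.** No sample size, power or alpha figure is involved. The check is one of logic.

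**Inputs.** The default, the exception, the five bullets and the definitions of prior and concomitant come from Section 7.6. The parallel list comes from Section 9.3. One illustrative assumption is added: a run-in start in mid-June 2017. Only the order of the dates matters.

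**Method.** Ten incomplete end-date patterns were classified in three ways:

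- *Literal:* a pattern that meets a bullet falls under the exception and is prior; otherwise the default applies and it is concomitant.
- *Inclusion:* a pattern that meets a bullet is concomitant; otherwise it is prior.
- *Definition:* the pattern is concomitant if the end date could lie on or after run-in start, and prior if it cannot.

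| End-date pattern | Meets a bullet | Literal | Inclusion | Definition |
|---|---|---|---|---|
| Year only, earlier year | no | concomitant | prior | prior |
| Year only, same year | yes (1) | prior | concomitant | concomitant |
| Year only, later year | yes (1) | prior | concomitant | concomitant |
| Month and year, earlier year | no | concomitant | prior | prior |
| Month and year, same year, earlier month | no | concomitant | prior | prior |
| Month and year, same month | yes (3) | prior | concomitant | concomitant |
| Month and year, later month | yes (3) | prior | concomitant | concomitant |
| Month and year, later year | yes (2) | prior | concomitant | concomitant |
| Year missing | yes (4) | prior | concomitant | concomitant |
| Wholly missing | yes (5) | prior | concomitant | concomitant |

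**Result.** The literal reading conflicts with the definition in 7 + 3 = 10 of 10 patterns. Seven that should be concomitant become prior, and three that clearly ended before the run-in become concomitant. The inclusion reading conflicts in 0 of 10.

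**Phase check.** Suppose the run-in starts on 25 March and Week 0 is 14 days later, on 8 April.

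- End date March: bullet 3 makes the drug concomitant, and it may indeed have been taken in the run-in. It was not ongoing at Week 0 and was not taken after it, so the double-blind definition excludes it from that phase.
- End date April: the drug may have stopped before or after 8 April. The bullets refer only to the run-in start and do not say how to assign the double-blind phase.

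**The case against.** The strongest reply is that the inverted reading defeats itself. The exception applies only where a date clearly shows a stop before treatment, and no bullet passes that test. The default in the same sentence, the definitions in the same section and the list in Section 9.3 all point to the intended meaning. This stands: a careful programmer would code the rule correctly, and harm arises only if it is coded as punctuated.

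The reach is also small. All prior and concomitant medications remain in Listing 16.2.4.4. No efficacy model uses this classification. The Alzheimer's medication subgroup has its own baseline definition in Section 7.5, and per-protocol exclusions are decided at the blinded data review (Sections 5.4 and 7.2).

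Two stronger readings are tempting, and the SAP supports neither.

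- A reader might infer that drugs stopped during the run-in are counted as double-blind use, because the bullets cite only the run-in start. The per-phase definitions already exclude such a drug, as the March example shows. What remains open is the date that straddles Week 0.
- A reader might infer that drugs still in use, which have no end date, become prior. A drug recorded as ongoing is concomitant by definition. The problem concerns records whose end date is missing or partial.

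**Conclusion.** The lead-in to the bullets in Section 7.6 is wrong as written, and the wording should be corrected. Read literally, it inverts the rule for all 10 patterns tested, in both directions. Severity is low, because the intent can be recovered from the SAP itself and the exposure is confined to the descriptive concomitant medication summary, Table 14.1.4.

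The 10 of 10 result counts types of date, not records. The SAP does not say how many medication records have incomplete end dates, so the effect on the table cannot be sized. The conclusion assumes that the definitions of prior and concomitant in Section 7.6 govern, which the parallel list in Section 9.3 supports.

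**What to change.** 1. Keep the default sentence, but let it refer to the start of treatment *in the run-in* and end it there with a full stop.
2. Introduce the five bullets with a new lead-in: *In particular, a medication with an incomplete end date will be considered concomitant if:*
3. Add one sentence on phase: the per-phase definitions in this section assign the phase, and a partial end date that could fall on or after the start of double-blind treatment counts as concomitant in that phase.

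Do not add a closing rule that every other case is prior. A record with day and year known but month missing meets none of the bullets. In the run-in year, or a later one, such a closing rule would make it prior, whereas the present default keeps it concomitant.

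The cost is a few lines of SAP text and a check of one derivation. No new data are needed. The straddling-date rule is conservative: it may count some drugs in the double-blind phase that had in fact stopped shortly before Week 0.

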7.7. SCANS

CT/MRI scans results and PET/CSF results will be recorded at Screening (Visit 1). This data will be listed only on the safety analysis set.

8. EFFICACY

8.1. PRIMARY EFFICACY ENDPOINT AND ANALYSIS

The primary efficacy endpoint is the change from baseline over 26 weeks of cNTB global composite score.

The global composite score of the cNTB is a composite score of the ISLT (immediate and delayed recall), OCL, IDN, DET, OBK and paper-based COWAT and CFT tests.

Calculation of scores: for each test listed above a z-score relative to study baseline will be calculated.

$$z - Score (z_{ijt}) = \frac{(x_{ijt} - \bar{x}_{1t})}{\sigma_{1t}} * Multiplicand$$

Where:

t = is the test indicator (ISLT, ISLT delayed, OCL, IDN, DET, OBK, COWAT or CFT)

i = indexes subject i

j = indexes the jth assessment for subject i (j = 1 means baseline)

x = cognitive score

x_{ijt} = subject's score for test t at the current assessment

\bar{x}_{1t} = mean performance score of the study sample for test t at baseline

σ_{1t} = standard deviation of the study sample for test t at baseline

Multiplicand equals 1 for tests for which a higher score is indicative of better cognitive performance (i.e., ISLT, ISLTR, OCL, COWAT, CFT) and -1 for tests where a lower score is indicative of better cognitive performance (i.e., IDN, DET, OBK)

Calculation of composite global score: A z-score for each test will be calculated as described above. A mean of all available z-scores for given patient in a given assessment will be calculated as the composite global score. For a given patient at a given assessment a minimum of 5 valid test scores of the tests listed above will be determined, of which at least 1 test are included from each of the domain composites as described in [Section 3.2](#).

cNTB global composite scores and changes from baseline will be summarized (by treatment) at Visits 2, 3, 4 and 5. Change in cNTB global composite scores from baseline over 26 weeks (Visit 5) will be analyzed using a MMRM model utilizing all baseline and postbaseline data to assess any differences in treatment effects over time. The model will include fixed effects of treatment, study site, visit, and treatment by visit interaction, with baseline score, age, gender and ApoE4 as covariates, and a baseline by visit interaction. The global treatment effect estimates will be reported, with 95% confidence intervals and P values. Baseline will be the last non-missing observation at Visit 2 or before. The standard error of the change from baseline will also be included. The adjusted mean difference between treatments versus placebo will be presented along with the standard error and a 95% confidence interval.

These analyses will be performed by using PROC MIXED in SAS, and adjusted means will be obtained by using the LSMEANS statement.

An effect size calculation will be performed, where Cohen's d effect size will be calculated on the adjusted mean difference of change from baseline of treatment versus placebo. The effect size will be derived as the adjusted mean difference divided by the pooled standard deviation. The pooled within group variance (standard deviation squared) of two treatments is defined as:

$$\text{Pooled Variance} = [(n1 - 1)*\text{Var1} + (n2 - 1)*\text{Var2}] / (n1 + n2 - 2)$$

Where:

n1 = number of subjects with non-missing data for Placebo at Week 26

Var1 = variance for Placebo

n2 = number of subjects with non-missing data for active treatment at Week 26

Var2 = variance for active treatment

These analyses will be performed on the full analysis set and additionally on the per protocol set as a supportive analysis.

A supportive efficacy analysis will be carried out using an ANCOVA method where the change in cNTB global composite scores from baseline to Week 26 will be the outcome variable and treatment group and study site will be main effects. cNTB global composite scores at baseline, age, gender, and ApoE4 will be included as covariates. The standard error of the change from baseline will also be included. Missing data (at the level of the composite score, not at the level of the individual tests) will be imputed using a pattern mixture model approach. Four patterns of missing data will be considered and imputed independently as follows:

- Pattern 1: will include patients who completed treatment on study drug (any missing data here is considered missing at random);
- Pattern 2: will include patients who discontinue treatment early due to adverse events (AEs);
- Pattern 3: will include patients who discontinue treatment early due to lack of therapeutic efficacy (LOTE);
- Pattern 4: will include patients who discontinue treatment early due to reasons other than AE event or LOTE.

The pattern mixture model methodology will be implemented using SAS procedures MI and MIANALYZE. Specifically, the following steps will be followed:

- Intermittent missing data will first be imputed using the Markov Chain Monte Carlo (MCMC) method implemented with the SAS MI procedure, which is appropriate for non-monotonic missing data.
- Data for patients who discontinue early will be multiply imputed as follows:
 - If the patient discontinues due to an AE (Pattern 2) or LOTE (Pattern 3), then missing data will be assumed to follow a distribution similar to the baseline values observed in the placebo arm of the study;
 - If the patient discontinues due to reasons other than an AE or LOTE (Pattern 4), at each time point, missing data will be assumed to follow a distribution similar to scores for patients that are still in the study and randomized to the same treatment group.
- Results of the ANCOVA on the multiply imputed data will be summarized using the SAS procedure MIANALYZE.

These analyses will be performed on the full analysis set and additionally on the per protocol set as a supportive analysis.

